5.7.2. Clinical Laboratory Measurements

A treatment-emergent Potential Clinically Significant abnormal value (PCSV) is a laboratory value that was normal at Screening and Baseline but clinically significantly abnormal after treatment with investigational product, or a laboratory value that was abnormal at Baseline and exacerbates after treatment with investigational product. “Exacerbations” will be identified by the Medical Monitor using clinical judgment.

Baseline clinical laboratory analytes and change from Baseline in clinical laboratory analytes to each scheduled assessment time will be summarized with descriptive statistics. Summary statistics will include the number of patients, mean, median, standard deviation, quartiles, minimum, and maximum. The graphs of mean (or median) value of some lab parameter vs. visit will also be plotted.

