#### **6.2.2. Exclusion Criteria**

A patient who meets any of the following criteria will be excluded from the study:

1. Patients who experience a  $\geq 10\%$  fall in FEV1 at 3 consecutive spirometry measurements during the placebo challenge
2. Positive human immunodeficiency virus (HIV) test
3. Positive hepatitis test (HBsAg and hepatitis C antibody)
4. History of significant multiple and/or severe allergies (including latex gloves) or has had an anaphylactic reaction or significant intolerance to prescription or nonprescription drugs or food
5. Participation in a prior REGN1908-1909 clinical trial
6. History of severe anaphylactic or severe asthmatic reactions to cat exposure
7. Active lung disease other than asthma
8. Treatment with an investigational drug within 2 months or within 5 half-lives (if known), whichever is longer, prior to screening
9. Persistent chronic or recurring acute infection requiring treatment with antibiotics, antivirals, or antifungals, or any untreated respiratory infections within 4 weeks prior to screening
10. Serum creatinine, creatinine phosphokinase (CPK), alkaline phosphatase, hepatic enzymes (aspartate aminotransferase [AST] and alanine aminotransferase [ALT]), total bilirubin (unless the Investigator has evidence that increased indirect bilirubin corresponds to a Gilbert's-type syndrome) that exceed 1.5 x the upper limit of normal (1.5 x ULN), or any laboratory findings showing evidence of organ dysfunction or any clinically significant deviation from the normal range, as decided by the Investigator at the screening visit
11. Any medical illness, which in the judgment of the investigator could preclude participation in the study or in whom treatment with epinephrine or beta-2 agonists or systemic corticosteroids would pose an increased risk (eg, history of cardiovascular disease, hypertension, diabetes, etc.)
12. Patients taking any prohibited treatment (Section [7.8.1](#) Prohibited Medications)
13. Use of systemic corticosteroids within 8 weeks prior to screening visit 1
14. Use of anti-IgE or other biological therapy within 6 months prior to screening visit 1

15. History of SIT with cat allergen or vaccines against cat allergy within 5 years of screening visit 1
16. SIT with any allergen within 6 months prior to screening visit 1

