##### Laboratory Tests

Laboratory test results will be summarized by baseline and change from baseline to each scheduled assessment time with descriptive statistics.

Number and percentage of patients with a potentially clinically significant value (PCSV) at any post-randomization time point will be summarized for each clinical laboratory test.

Shift tables based on baseline normal/abnormal and other tabular and graphical methods may be used to present the results for laboratory tests of interest.

Listings will be provided with flags indicating the out-of-laboratory range values.

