2.3. Study Plan

Study patients, the principal investigators, and study site personnel (with the exception of the study pharmacist) will be blinded to all randomization assignments throughout the study. The Regeneron Study Director, Medical Monitor, Study Monitor, and all other Regeneron personnel who will be in regular contact with the study site will be blinded to all patient randomization assignments. Study drug kits coded with a medication numbering system will be used. In order to maintain the blind, lists linking these codes with product lot numbers will not be accessible to blinded individuals involved in study conduct. Although the designated study

pharmacist(s)/designee at the study site are unblinded, the treatment assignment will not be provided to site personnel, including the investigator, at any time during the conduct of the study, except in the case of a true emergency.

Selected individuals who are not responsible for the treatment or clinical evaluation of patients may have access to unblinded data as needed for safety review or other data review.

The Study event table is presented in Section [10.2](#).

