6.1. Definition of Baseline for Efficacy/Safety Variables

Unless otherwise specified, the Baseline assessment for all measurements will be the latest available valid measurement taken prior to the administration of investigational product.

If the scheduled Baseline Day 1 measurements are not available, screening assessments may be used.

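### SAP 5.7.2 defines a treatment-emergent laboratory PCSV more narrowly than the protocol's count, so a value abnormal at Screening and normal at Baseline can never qualify

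*SAP*

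**What the plan says.** SAP 5.7.2 gives two ways for a laboratory value to be a treatment-emergent PCSV. The first is "a laboratory value that was normal at Screening and Baseline but clinically significantly abnormal after treatment with investigational product". The second is "or a laboratory value that was abnormal at Baseline and exacerbates after treatment with investigational product". The rule sets no numeric criterion for worsening; instead, such cases "will be identified by the Medical Monitor using clinical judgment". Numeric limits are listed in SAP Appendix 10.3, to which SAP 5.7 refers for PCSV thresholds.

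Under SAP 6.1, "the Baseline assessment for all measurements will be the latest available valid measurement taken prior to the administration of investigational product". That is normally the Day 1 sample, drawn separately from the Screening visit 1 sample.

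Protocol 10.4.4.2 (Laboratory Tests) covers every laboratory analyte and sets no pre-dose condition: "Number and percentage of patients with a potentially clinically significant value (PCSV) at any post-randomization time point will be summarized". It also calls for listings that flag out-of-range values.

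SAP 5.7.3, under the vital signs heading, promises a summary of PCSVs and then optional shift tables for laboratory tests of interest. It does not say whether that summary uses the treatment-emergent definition.

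**The concern.** The two branches do not cover every pre-dose state. A patient whose analyte was out of range at Screening and back in range on Day 1 cannot have a treatment-emergent PCSV for that analyte, however extreme the later value. For example, a CPK of 1.4 x ULN at Screening, normal on Day 1 and above 10 x ULN on Day 29 would not be counted. The Screening condition has no evident purpose, because Baseline is already the last pre-dose value and the Screening sample can be up to 85 days old.

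For values abnormal at Baseline, the count cannot be reproduced from the data, although Appendix 10.3 supplies limits that could be applied.

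The protocol promises a broader count that the SAP does not restate, and the SAP's list of changes from its Version 1 does not mention narrowing it. The treatment-emergent definition is the SAP's only laboratory PCSV counting rule, so a programmer could reasonably apply it to the PCSV table. At stake is the accuracy of one descriptive table serving the secondary safety objective.

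**Working it through.** The plan states no figure to reproduce. The check applies both rules to each pre-dose state and then bounds the size of the gap.

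**1. Which states are counted.** Assume a post-dose value that meets an Appendix 10.3 limit.

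| Screening | Baseline | SAP 5.7.2 | Protocol 10.4.4.2 |
|---|---|---|---|
| normal | normal | counted | counted |
| normal | abnormal | only if judged an exacerbation | counted |
| abnormal | normal | not counted | counted |
| abnormal | abnormal | only if judged an exacerbation | counted |

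The SAP counts one state of four on the threshold alone; the protocol counts all four. Conditioning the first branch on Baseline alone would bring the third row in. If the Day 1 sample is missing the gap need not arise, since SAP 6.1 adds: "If the scheduled Baseline Day 1 measurements are not available, screening assessments may be used".

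**2. Can the third row contain patients?** Exclusion criterion 10 removes patients whose named analytes are above 1.5 x ULN, and any deviation the investigator considers clinically significant. Milder abnormalities can therefore pass. Footnote 10 to the schedule of events requires screening safety assessments to be normal before dosing, which read literally would nearly empty the row. The two texts disagree, so the row is narrowed but not reliably closed.

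**3. Patients in the third row, one analyte.** The documents give no rate, so the share p is an assumption. Expected number = 60p; chance of at least one = 1 - (1 - p)^60.

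| p | expected of 60 | chance of at least one |
|---|---|---|
| 1% | 0.6 | 45% |
| 2% | 1.2 | 70% |
| 5% | 3 | 95% |
| 10% | 6 | 99.8% |

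**4. Patients in the third row, 15 parameters.** Appendix 10.3 has limits for 15 parameters that the protocol collects: ALT, AST, alkaline phosphatase, total bilirubin, CPK, creatinine, uric acid, sodium, potassium, glucose, WBC, neutrophils, eosinophils, hemoglobin and platelets. Assume a 95% reference range, bivariate normal Screening and Day 1 values, and independent parameters. Then p = P(|x| > 1.96 and |y| <= 1.96), and the chance of at least one such parameter is 1 - (1 - p)^15.

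| Screening to Day 1 correlation | p, two-sided | at least one of 15 | p/2, one-sided | at least one of 15 |
|---|---|---|---|---|
| 0.5 | 4.07% | 46% | 2.04% | 27% |
| 0.7 | 3.35% | 40% | 1.67% | 22% |
| 0.85 | 2.46% | 31% | 1.23% | 17% |

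The one-sided columns matter because many Appendix 10.3 limits are upper limits only. All these figures ignore screening exclusions and the correlation between analytes such as ALT and AST.

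**5. Values actually omitted.** An omission also needs a post-dose PCSV in the same parameter. Let q be that rate per parameter, assumed to be 0.5% to 2% and independent of the pre-dose state. Expected omissions = 60 x 15 x p x q.

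- Low end: 60 x 15 x 0.0246 x 0.005 = 0.11.
- High end: 60 x 15 x 0.0407 x 0.02 = 0.73.

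These use the two-sided p; the one-sided p halves them. For scale, one patient in an arm of 30 is 1/30 = 3.3 percentage points.

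**The case against.** The strongest reply is that no SAP output is expressly tied to the treatment-emergent definition. SAP 5.7.3 plans a PCSV summary without that qualifier and follows it with shift tables, the same order as the protocol's laboratory paragraph. It may simply be the protocol's unfiltered count under the wrong heading. This stands as a plausible reading, but it leaves the definition unstated, which is part of the point.

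Three stronger readings are tempting, and the documents do not support them.

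- **Serious shifts would go unseen.** Listings flag out-of-range values, and SAP 5.7.2 reports minimum and maximum for laboratory values by visit. Protocol 8.2.3.6 requires significantly abnormal post-treatment results to be repeated, and medically relevant abnormalities can be recorded as adverse events. These routes show the value, but none guarantees the protocol's patient count: shift tables are optional, and an asymptomatic abnormality need not become an adverse event.
- **A third or more of patients would have uncounted events.** The 31% to 46% above describes patients with at least one parameter in the uncovered state, under generous assumptions. It is not a rate of omitted PCSVs.
- **The judgment step biases the comparison.** On treatment allocation, SAP 2.3 says the "Medical Monitor, Study Monitor, and all other Regeneron personnel who will be in regular contact with the study site will be blinded". The weakness is reproducibility, not bias by treatment. Judgment can also pick up worsening that a fixed threshold would miss.

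**Conclusion.** The point holds in limited form. On its wording, SAP 5.7.2 cannot count a value abnormal at Screening and normal at Baseline, and it gives no numeric criterion for worsening from an abnormal Baseline. It is narrower than Protocol 10.4.4.2, and SAP 5.7.3 leaves open which definition governs the PCSV summary.

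The practical effect is probably below one omitted value in the whole trial. That figure rests on the assumed correlations of 0.5 to 0.85, independence between parameters, and the assumed PCSV rate of 0.5% to 2% per parameter. It covers only the third row of the table; the effect of the judgment step cannot be quantified from the documents. The primary analysis, alpha and power are untouched. The case for changing the text is that the correction is cheap and makes the safety table match the protocol.

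**What to change.** 1. In SAP 5.7.2, remove the Screening condition. Word the first branch as a value that did not meet the Appendix 10.3 criterion at Baseline (the last pre-dose value) and meets it after dosing.
2. State in SAP 5.7.2 that the number and percentage of patients with any post-randomization laboratory PCSV, regardless of pre-dose status, will be tabulated by treatment group, as in Protocol 10.4.4.2.
3. For values already meeting a criterion at Baseline, keep the blinded Medical Monitor review of exacerbation, and flag every move to a higher Appendix 10.3 category where more than one is listed (for example, ALT from above 3 to above 5 x ULN). A category move should not replace the review: alkaline phosphatase, eosinophils and platelets have only one listed category, so real worsening in them could never be counted.
4. Reconcile footnote 10 of the schedule of events with exclusion criterion 10 on mildly abnormal Screening values.

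The cost is a paragraph in the SAP, the reconciliation of the two eligibility texts, and a few more values in the safety tables.

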5.7.3. Analysis of Vital Signs

Vital signs (temperature, pulse, blood pressure, and respiration rate, and oximetry) will be summarized by Baseline and change from Baseline to each scheduled assessment time with descriptive statistics. The graphs of mean (or median) value of some vital sign parameter vs. visit will also be plotted.

A summary of PCSVs will be constructed. Shift tables based on baseline normal/abnormal and other tabular and graphical methods may be used to present the results for laboratory test of interest.

5.7.4. Analysis of 12-Lead ECG

ECG parameters (P-R interval ,QT interval, QTc interval, QRS interval, Ventricular rate and Heart rate) will be summarized at Baseline by treatment group.

5.7.5. Physical Exams

The number (n) and percentage (%) of subjects with abnormal, clinically significant physical exams will be summarized at each scheduled assessment time by treatment. Listings of physical examinations will be provided, including comments if examination was not performed. Listings of clinically significant abnormal physical examinations for each patient will be provided, along with comments from the investigator describing these abnormalities. These abnormalities will be organized into physical system classifications.

5.8. Analysis of Pharmacokinetic Data

Descriptive statistics of total REGN1908, total REGN1909 and total antibody (REGN1908+REGN1909) at each sampling time will be provided. Plots of mean concentrations versus time will be presented.

5.9. Analysis of Immunogenicity Data

The immunogenicity variables described in Section 4.8 will be summarized using descriptive statistics. Analysis described in this section will be performed separately for ADA against REGN1908 and ADA against REGN1909 in all treatment groups unless otherwise specified.

Immunogenicity will be characterized by ADA responses and titers observed in patients in the ADA analysis set. ADA response categories and titer categories are defined as follows:

ADA response categories:

- Pre-existing immunoreactivity, defined as either an ADA positive response in the ADA assay at baseline with all post first dose ADA results negative, OR a positive response at baseline with all post first dose ADA responses less than 9-fold over baseline titer levels.
- Treatment-emergent response, defined as a positive response in the ADA assay post dose when baseline results are negative or missing.
- Treatment-boosted response, defined as a positive response in the ADA assay post first dose that is greater than or equal to 9-fold over baseline titer levels, when baseline results are positive

Titer categories (Maximum titer values)

- Low (titer <1,000)
- Moderate (1,000 ≤ titer ≤ 10,000)
- High (titer >10,000)

The following analysis will be provided:

- Number (n) and percent (%) of ADA-negative patients (pre-existing immunoreactivity or negative in the ADA assay at all time points) by treatment groups
- Number (n) and percent (%) of treatment-emergent ADA positive patients by treatment groups and ADA titer categories
- Number (n) and percent (%) of treatment-boosted ADA positive patients by treatment groups and ADA titer categories

Listing of all ADA titer levels will be provided for patients with pre-existing, treatment-emergent, and treatment-boosted ADA response.

5.9.1. Association of Immunogenicity with Exposure, Safety and Efficacy Immunogenicity and Exposure

Potential association between ADA variables and systemic exposure to REGN1908 or REGN1909 will be explored separately by treatment groups. Plots of drug concentration may be provided for analyzing the potential impact of ADA response status and titer on PK.

Immunogenicity and Safety and Efficacy

Potential association between ADA variables and safety may be explored with a primary focus on the following safety events during the TEAE period:

- Injection site reaction (serious or severe and lasting 24 hours or longer)
- Hypersensitivity (SMQ: Hypersensitivity [Narrow])
- Anaphylaxis (SMQ: Anaphylaxis [Narrow])

Potential association between ADA variables and efficacy endpoints may be explored (e.g. scatter plot or spaghetti plot).

The safety and efficacy analyses mentioned above will be conducted using the following categories:

- ADA positive patients, that is patients with treatment-emergent or treatment-boosted response.
- ADA negative patients, that is patients with pre-existing immunoreactivity or negative in the ADA assay at all time points.

Maximum post-baseline titer in treatment-emergent or treatment-boosted ADA positive patients:

- Low (titer <1,000)
- Moderate (1,000 ≤ titer ≤ 10,000)
- High (titer >10,000)

5.10. Analysis of Biomarker Data

All biomarker analyses will be performed on the FAS using all observed data. Descriptive statistics for the observed values and change and percent change from baseline in detectable IgE (or percent of detectable IgE compared to baseline) by treatment and visit will be provided for the biomarker variables.

The percent of detectable IgE at each visit compared to baseline, and the ratio of Fel d 1 IgE to Cat Dander IgE at baseline will also be correlated to the primary and secondary clinical efficacy endpoints using Spearman's rho test. Both the Spearman correlation coefficients and p-values will be reported.

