## 2.3. Exploratory Objective(s)

### 2.3.1. Exploratory Efficacy Objectives

- To evaluate LAR on days 8, 29, 57, and 85
- To evaluate whether a single prophylactic SC administration of REGN1908-1909 inhibits a wheal-and-flare response to a skin prick test with serial allergen titration with cat allergen in patients with cat allergen-triggered asthma and AR with or without conjunctivitis on days 29 and 85
- To evaluate the prophylactic efficacy of REGN1908-1909 in cat-allergic patients not living with a cat to reduce respiratory symptoms induced by a Controlled Cat Allergen Challenge on days 8, 29, 57, and 85 as measured by chest symptom questions
- To assess the prophylactic effect of REGN1908-1909 on biochemical measures of asthma control (FeNO) in patients with cat allergen-triggered asthma induced by a Controlled Cat Allergen Challenge on days 30 and 86 and measured 24 hours after challenge
- To assess the prophylactic effect of REGN1908-1909 on TNSS, TOSS, and chest symptoms up to 24 hours after leaving the EEU
- To assess the prophylactic effect of REGN1908-1909 on objective measures of nasal congestion (PNIF) in patients with cat allergen-triggered asthma induced by a Cat Allergen Challenge on 8, 29, 57, and 85
- To assess the relationship between baseline cat allergen-specific IgE levels (cat hair sIgE, Fel d 1 sIgE), total IgE, and the ratio of cat allergen-specific IgE/total IgE (cat hair sIgE/total IgE and Fel d 1-specific IgE/total IgE levels) and efficacy of REGN1908-1909
- To assess the relationship between cat allergen-specific IgE levels (Fel d 2, Fel d 4, Fel d 7, and other common allergens) at screening and baseline to evaluate the relationship between response to REGN1908-1909 and poly/mono-sensitization
- To assess the extent of REGN1908-1909 interference with the measurement of endogenous anti-Fel d1 IgE in baseline samples and its relationship to clinical benefit
- To assess the degree to which REGN1908-1909 prevents induction of type 2 inflammation in the nasal mucosa as assessed by RNA sequencing of nasal brushing on day 29.

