3.1. The Full Analysis Set (FAS)

FAS includes all randomized subjects who receive any investigational product and have completed the Day 8 Cat Allergen Challenge. Efficacy analyses will be based on the treatment allocated by the IVRS at randomization (as randomized).

FAS is the primary analysis set for efficacy endpoints.

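### Post-dose detectable IgE is correlated with efficacy on the two-arm FAS without regard to arm, so the treatment effect alone can make the correlation significant

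*SAP*

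**What the plan says.** SAP 5.10 opens with the analysis set: "All biomarker analyses will be performed on the FAS using all observed data". SAP 3.1 defines that set without regard to arm: "FAS includes all randomized subjects who receive any investigational product and have completed the Day 8 Cat Allergen Challenge".

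The descriptive IgE summaries are split by arm: "or percent of detectable IgE compared to baseline) by treatment and visit will be provided for the biomarker variables". The correlation comes next and names two quantities: "The percent of detectable IgE at each visit compared to baseline, and the ratio of Fel d 1 IgE to Cat Dander IgE at baseline". These "will also be correlated to the primary and secondary clinical efficacy endpoints using" Spearman's rho, and "Both the Spearman correlation coefficients and p-values will be reported". The by-arm wording is not repeated, and no treatment term, stratification, significance level or sidedness is given.

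Elsewhere the SAP does say when arms are to be kept apart. In SAP 5.9.1 the association of anti-drug antibodies with exposure "will be explored separately by treatment groups".

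SAP 4.9 lists IgE only at screening and baseline. The schedules of events and Protocol 4.6 provide for IgE sampling at each post-dose challenge visit, so the post-dose variable in SAP 5.10 will exist.

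**The concern.** Followed as written, SAP 5.10 puts placebo and drug patients into one rank correlation of a post-dose marker with a post-dose outcome. If treatment moves both, placebo patients sit at high IgE with short times to EAR, and drug patients at low IgE with long times. The coefficient then partly restates the treatment effect. It does not show that, among treated patients, those with a larger fall in detectable IgE did better.

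The antibodies bind Fel d 1 and are designed to block its binding to IgE (Protocol 1). An effect on measured IgE is therefore most plausible for Fel d 1 and cat hair IgE. The documents give no comparable reason for Fel d 2, 4 or 7.

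At stake is a reported p-value that a reader could take as evidence of a biomarker-response relation that the data need not contain.

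**Working it through.** **Plan's own figure.** SAP 2.2 states 84% power: log-rank test, hazard ratio 0.44, one-sided 0.05, 30 per arm, 8 dropouts (26 per arm left). With exponential times and censoring at 240 minutes:

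- Event probability on placebo: 1 − 2^(−240/58) = 0.943. On drug: 1 − 2^(−240/132) = 0.716.
- Expected events: 26 × (0.943 + 0.716) ≈ 43.2.
- Schoenfeld power: Φ(√43.2 × 0.5 × |ln 0.44| − 1.645) = Φ(1.05) ≈ 0.85.

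This is within 2 points of 84%, so these inputs are a fair model of the planned effect. The SAP gives no figure for the Spearman analysis.

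**Inputs from the documents.** Medians 58 and 132 minutes, 26 or 30 per arm (SAP 2.2); censoring at 4 hours (SAP 5.6); spirometry every 10 minutes (SAP 4.5.2).

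**Assumptions.** Percent detectable IgE is normal with SD 20 points, mean 100 on placebo and 80, 60 or 30 on drug (shifts of 1, 2 and 3.5 SD). It is independent of time to EAR within each arm. The test is two-sided at 0.05. Times censored at 4 hours enter as tied values at 240 minutes, because SAP 5.10 has no rule for them.

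**Tests compared.**
- Pooled: Spearman's rho over all patients, t = rho × √((N−2)/(1−rho²)) on N−2 degrees of freedom.
- Adjusted: rank all patients, subtract the arm mean rank from both variables, correlate the residuals, and refer to t on N−3 degrees of freedom.
- Drug arm alone: Spearman's rho in that arm.

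**Share of simulated trials with p < 0.05** (20,000 trials per setting, 26 per arm; simulation error at most about 0.4 points, one standard error):

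| Drug-arm IgE mean | Mean pooled rho | Pooled | Adjusted | Drug arm alone |
|---|---|---|---|---|
| 100% (no shift) | 0.00 | 5% | 5% | 5% |
| 80% | −0.15 | 19% | 5% | 5% |
| 60% | −0.24 | 41–42% | 5% | 5% |
| 30% | −0.28 | 54% | 5% | 5% |

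At 30 per arm the pooled rates for 80%, 60% and 30% are 21%, 48% and about 60%. With no drug effect on EAR (58 minutes in both arms) the pooled rate is about 5% at every IgE shift.

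**Other endpoints and visits.** For FEV1 AUC, the plan's 27 versus 15 at 88% power implies a standardised difference of (1.645 + 1.175) × √(2/30) ≈ 0.73. The pooled rate is then 19–58% at 26 per arm, for IgE shifts from 1 SD to complete separation. For time to EAR over the four challenge visits, assume the planned effect at each visit and a within-patient correlation of 0.5. The chance of at least one significant pooled result is 78–87% for shifts of 2 SD or more, against about 18% when stratified by arm.

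**The case against.** **Pooling is inferred.** The by-arm descriptive summaries also use the FAS, so naming the FAS does not by itself mean that arms are merged. That is fair. But the correlation sentence has no arm qualifier, while its neighbour and SAP 5.9.1 do. An analyst following the text would pool, and if within-arm analysis is meant, the text does not secure it.

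**No document states a post-dose fall in IgE.** A reader might infer that the protocol expects one. It does not. The objective in Protocol 2.3.1 is "To assess the extent of REGN1908-1909 interference with the measurement of endogenous anti-Fel d1 IgE in baseline samples", and the assay in Protocol 4.6 uses serum taken before dosing to find out whether the drug blocks IgE binding. This makes an effect plausible but gives no size for it. The assumed range must stay visible.

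**The baseline ratio.** A reader might extend the criticism to the baseline Fel d 1 to cat dander IgE ratio in the same sentence. Treatment cannot alter a baseline value, so this mechanism does not reach it. SAP 5.6.1 also explores the Fel d 1 ratio as a covariate in the Cox model and as a possible subgroup factor.

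**Limited consequence.** No decision rule depends on these correlations, and Protocol 10.4.3.3 disclaims multiplicity control for secondary and exploratory endpoints. This limits the weight of the point. It does not make the pooled p-value interpretable.

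**Within-arm estimates are weak.** With 26 patients, two-sided significance needs |rho| of about 0.39, and 80% power needs about tanh((1.96 + 0.84)/√23) ≈ 0.53. Uniform suppression of IgE on drug would narrow the range further. This favours the treatment-adjusted correlation as the main result over reliance on the drug arm alone.

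**Conclusion.** The point holds as a possibility. On the FAS without regard to arm, the correlation of post-dose detectable IgE with efficacy can be significant through treatment alone. At the planned effect and 26 per arm the chance per test is about 19%, 41% and 54% for assumed drug-arm IgE means of 80%, 60% and 30% of baseline, against a nominal 5%. These figures rest on the assumed IgE shift and SD, on reading SAP 5.10 as pooled, and on a two-sided 0.05 test.

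A reader might go further and infer that a significant correlation is assured. The figures do not support that: even complete separation of the arms on IgE gives only 55–56% per test at the planned effect, and there is no excess unless the drug moves both variables. Nor does the point touch the primary comparison or the baseline ratio. It concerns how an exploratory biomarker result can be read, and it is worth correcting because the correction is small.

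**What to change.** In SAP 5.10, state that correlations of post-dose percent detectable IgE with efficacy endpoints will be partial rank correlations adjusted for treatment, or Spearman correlations stratified by treatment, shown with the estimate and interval in each arm. State also that a pooled unadjusted p-value will not be reported as evidence of a biomarker-response relation.

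The change is one or two sentences and needs no new data. SAP 1 allows revision on blinded review before data lock and code breaking. The adjusted version keeps patients from both arms. The cost falls on the within-arm estimates, which rest on about 26 to 30 patients each: for a true rho near zero, the 95% interval is roughly ±0.39 at 26 and ±0.36 at 30 (tanh(1.96/√(n−3))).
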